12 OCT2020

## **9 RANDOMIZATION AND BLINDING PROCEDURES**

### **9.1 Randomization**

Patients will be randomized in a 1:1 ratio to receive AP01 either 50 mg once daily or 100 mg twice daily; both regimens being administered by the eFlow. The randomization schema will be stratified by region (Asia-Pacific and Europe) and by disease severity (FVC < 50% predicted and FVC ≥ 50% predicted). The first 20 patients randomized in the study must have FVC ≥ 50% predicted at Screening. After the first 20 patients have been randomized, patients with FVC 40% < 50% predicted will be allowed to be randomized in the study but randomization for these patients will be capped at 20.

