## 11.5 Efficacy and Safety Analyses

### 11.5.1 Efficacy Analyses

The following analyses will be performed:

- Change from Baseline in absolute FVC % predicted
- Change from Baseline in cough frequency as measured by LCM
- Change from Baseline in the total KBILD score and in KBILD breathlessness and activity domains
- Change from Baseline in the total LCQ score.
- Change from Baseline in cough severity as measured by VAS
- Change from Baseline in extent of fibrosis and lung volumes as assessed by HRCT
- Change from Baseline in  $D_{LCO}$

The primary endpoint of interest for efficacy is the absolute change from Baseline to Week 24 in FVC % predicted. Linear mixed-effects modeling will be used and differences between treatment arms will be examined. Baseline FVC, region and progression-related biomarker (CXCL13, CCL18, MMP3) values will be considered as covariates in the model. Further details on the assumptions and planned analyses will be provided in the SAP. Similar modeling strategies will be employed for longer term data obtained from Part B of the study. No control group is included in this study, however exploratory analyses will be conducted using registry and historical data as comparators. Details of all analyses will be provided in the SAP.

In order to assess the impact of treatment on cough in those patients for whom coughing is of greatest concern, additional analyses of cough frequency will be performed on the subset of patients with baseline cough severity VAS > 40 millimeters and in patients with baseline cough frequency  $\geq 10$  coughs/hour during awake hours.

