8.1. Primary Efficacy Endpoint and Analysis

Spirometry will be conducted at approximately the same time each visit (within 60 minutes of Day 1 spirometry measurement) with the patient in seated position. The test will be performed to American Thoracic Society/European Respiratory Society (ATS/ERS) guidelines³. On days of clinic visits (including the screening visit), patients must refrain from strenuous activity at least 12 hours prior to pulmonary function testing (PFT). FVC % predicted will be calculated using the ERS Global Lung Function Initiative 2012 equations² as outlined in the clinical study manual.

PFTs will be collected at Screening, Baseline and at each post-Baseline time point (Week 4, 8, 12, 16, 20, 24, 36, 48, 60, 72 and Follow-Up) as described in Section 6.1.

The primary efficacy endpoint is the change from baseline in absolute FVC % predicted from Baseline to Week 24. The population used for efficacy analyses of the primary variable will be the PP with the FAS used for the first sensitivity analyses.

A linear mixed-effects model (PROC MIXED) will be used and differences between treatment groups between slopes estimating the change from baseline in absolute FVC % predicted from Baseline to Week 24 will be examined. Baseline FVC % predicted, region, age at screening, sex, baseline DL_{CO} % predicted, and baseline progression-related biomarker (CXCL13, CCL18, MMP3) values each categorized as >Median level vs. ≤Median level will be included as covariates in the model. This analysis requires at least three post-baseline FVC % predicted values in addition to baseline be available for a patient to be included in the analysis so that the slope estimated is identifiable. Similar modeling strategies will be employed for longer-term data obtained from Part B of the study. Spirometry data collected after patients switched dosing regimen from 50 mg once daily to 100 mg twice daily will be omitted for this analysis.

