The following statistics for in-clinic FVC and FVC % Predicted will be calculated and summarized by treatment group and displayed in a table:

- Summary statistics of in-clinic FVC and FVC % Predicted at Baseline and at each post-Baseline time point (Week 4, 8, 12, 16, 20, 24, 36, 48, 60, 72 and Follow-Up)
- Summary statistics of in-clinic FVC and FVC % Predicted reflecting the absolute change from Baseline to each post-Baseline time point (Week 4, 8, 12, 16, 20, 24, 36, 48, 60, 72 and Follow-Up).

The following plot will be produced for in-clinic FVC and FVC % Predicted:

- Mean FVC (or FVC % Predicted) Change from Baseline (\pm SD) vs. Visit Week (Week 4, Week 8, Week 12, etc.) with lines for each treatment group.

Linear mixed-effects models (PROC MIXED) will be used for the analyses. The model will include the change from baseline in in-clinic FVC (or FVC % Predicted) (measured at any time in the study) as the dependent variable and will include patient and time (continuous) as random effects, fixed effect of time and time-varying effects for treatment group and treatment-by-time interaction to account for those patients who switched dosing regimens from 50 mg once daily to 100 mg twice daily in Part B. Longitudinal plots at selected timepoints displaying the model adjusted, least square means and 95% confidence intervals will be produced.

All in-clinic pulmonary function data will be presented in a listing.

8.2. Secondary Efficacy Endpoint(s) and Analyses**8.2.1. Change from baseline in cough frequency as measured by LCM**

The LCM⁴ is an audio-based cough detection device that allows sounds to be reconstructed and measured as cough events. Patients that pass all of the screening criteria and will be randomized in the study will be provided with a cough monitor to wear for a 24-hour period prior to coming in for their Baseline visit. This will be used as their baseline reading. The LCM and mailing materials will also be dispensed at Visits 5 and 8. Patients will wear for a 24-hour period, fill out the cough monitor paper diary

This document is confidential.

SAP Version: 3.0 (15JUL2021)
Controlled Document ID: **3903A.01**, Effective Date 29-Oct-2018
Filing requirements: TMF

Page 32 of 52

Statistical Analysis PlanSponsor: Avalyn Pharma, Inc.; Protocol No.: AP01-002

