8.2.6. Change from baseline in D_{LCO}

D_{LCO} will be collected at each visit. For predicted normal values, different sites may use different prediction formulas, based on the method used to measure D_{LCO} . In any case, the method used must be in compliance with the ATS/ERS guidelines⁵ on D_{LCO} measurements and the prediction formula appropriate for that method⁷. Raw data (gas mixture, equation used for prediction of normal, further adjustments made if so) must be traced.

PFTs will be collected at Screening, Baseline (pre-dose and post-dose) and at each Post-Baseline time point (Week 4, 8, 12, 16, 20, 24, 36, 48, 60, 72 and Follow-Up) as described in Section 6.1.

The following statistics for D_{LCO} and D_{LCO} % Predicted will be calculated and summarized by treatment group and displayed in a table:

- Summary statistics of D_{LCO} and D_{LCO} % Predicted at Baseline and at each post-Baseline time point (Week 4, 8, 12, 16, 20, 24, 36, 48, 60, 72 and Follow-Up)
- Summary statistics of D_{LCO} and D_{LCO} % Predicted reflecting the absolute change from Baseline to each post-Baseline time point (Week 4, 8, 12, 16, 20, 24, 36, 48, 60, 72 and Follow-Up).

The following plot will be produced for D_{LCO} and D_{LCO} % Predicted:

- Mean D_{LCO} (or D_{LCO} % Predicted) Change from Baseline (\pm SD) vs. Visit Week (Week 4, Week 8, Week 12, etc.) with lines for each treatment group.

A linear mixed-effects model (PROC MIXED) will be used for the analysis. The model will include the change from baseline in D_{LCO} (or D_{LCO} % Predicted) (measured at any time in the study) as the dependent variable and will include patient as a random effect, fixed effect of time and time-varying effects for treatment group and treatment-by-time interaction to account for those patients who switched dosing regimens from 50 mg once daily to 100 mg twice daily in Part B. To account for correlated repeated measures within patients a spatial power matrix will be used. Longitudinal plots at selected timepoints displaying the model adjusted, least square means and 95% confidence intervals will be produced.

All D_{LCO} data will be presented in a listing.

This document is confidential.

Statistical Analysis PlanSponsor: Avalyn Pharma, Inc.; Protocol No.: AP01-002

9. Exploratory**9.1. Correlation between weekly home spirometry measurements and in-clinic spirometry**

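### The only DLCO model and the all-study in-clinic FVC model omit the baseline value and the randomisation factors, and the primary slope model does not say in what form its covariates enter

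*SAP*

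**What the plan says.** - **DLCO (SAP 8.2.6).** The one model for change in DLCO "will include patient as a random effect, fixed effect of time and time-varying effects for treatment group and treatment-by-time interaction", with a spatial power covariance. It uses measurements from the whole study.
- **All-study in-clinic FVC (SAP 8.1, near the end).** The model "will include patient and time (continuous) as random effects, fixed effect of time and time-varying effects for treatment group and treatment-by-time interaction". It also uses all study time, including data after the switch from 50 mg once daily to 100 mg twice daily.
- **Randomisation (Protocol 9.1, repeated in SAP 3.6).** "The randomization schema will be stratified by region (Asia-Pacific and Europe) and by disease severity", the severity cut being FVC below 50% predicted against 50% or above. No more than 20 patients may be below 50%.
- **Other models in the SAP.** The cough frequency model (8.2.1) and the HRCT model (8.2.5) include the baseline value and region, together with age, sex, baseline DLCO and the biomarkers. The CA19-9/CA-125 model (9.4) includes the baseline value.
- **Primary slope model (SAP 8 and 8.1).** The SAP says that "differences between treatment groups between slopes estimating the change from baseline in absolute FVC % predicted from Baseline to Week 24 will be examined". It names baseline FVC % predicted, region, age, sex, baseline DLCO and three biomarkers, and ends the list with "values each categorized as >Median level vs. ≤Median level will be included as covariates in the model". Protocol 11.5.1 says only that the "values will be considered as covariates in the model".

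**The concern.** Change in DLCO is a stated objective and a secondary efficacy endpoint, yet its only model has no baseline DLCO term, while baseline DLCO is a covariate for cough and for HRCT. SAP 12, on changes from the protocol analysis, gives no reason. Using change from baseline as the outcome does not replace a baseline covariate: it fixes the coefficient of baseline instead of estimating it, so any association between baseline and change stays in the error term. Likewise, stratifying the randomisation and then ignoring the strata discards the precision that stratification was meant to buy.

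The primary slope model raises a related question. Its target is a difference in slopes. A covariate entered only as a main effect shifts a patient's level, not the rate of change. The SAP does not say whether its covariates are main effects or are crossed with time.

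At stake are the width of the between-arm intervals and the protection against chance imbalance, in a study of about 50 per arm meant to guide regimen selection.

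**Working it through.** **The plan's own figure.** SAP 3.5 gives SD 4.5 and 50 per arm, with a 95% half-width of 1.25 for one arm's mean change in FVC % predicted. Check: 1.96 × 4.5 / √50 = 1.247. It reproduces.

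**Baseline adjustment, illustrated on FVC.** No DLCO SD is given, so DLCO itself cannot be done. Let r be the correlation between baseline and change. The documents do not give r, so it is varied. Residual SD = 4.5 × √(1 − r²); between-arm half-width = 1.96 × residual SD × √(2/50).

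| assumed r | residual SD | half-width |
|---|---|---|
| 0 | 4.500 | 1.76 |
| 0.2 | 4.409 | 1.73 |
| 0.4 | 4.124 | 1.62 |

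The narrowing is 1 − √0.96 = 2.0% at r = 0.2 and 1 − √0.84 = 8.3% at r = 0.4. This is a single-time-point calculation, not the repeated-measures model itself.

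**Form of the covariate in a slope model.** Simulation of 600 trials, with assumed inputs:
- 50 per arm and visits at Weeks 4 to 24.
- True 24-week slope difference 2.4, the arm difference of 3.9 − 1.5 quoted in SAP 3.5.
- Random-slope SD 3.5 and residual SD 2.
- One covariate worth 2 points per SD on the 24-week slope, which is 4 / (4 + 3.5²) = 25% of the slope variance.

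| model | SD of estimated slope difference | shift per 1-SD covariate imbalance |
|---|---|---|
| free intercept, no covariate | 1.035 | 1.915 |
| free intercept, main effect | 1.035 | 1.915 |
| free intercept, covariate-by-time | 0.965 | −0.073 |
| slopes through the origin, no covariate | 0.979 | 1.950 |
| slopes through the origin, main effect | 0.959 | 1.684 |

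With a free intercept and complete visits, the main effect left the slope difference unchanged to rounding (largest difference about 2 × 10⁻¹⁵). A separate run in which 25% of patients lost visits gave a shift of 1.970 without the covariate and 1.971 with its main effect. The covariate-by-time term lowered the SD by 1 − 0.965/1.035 = 6.8%. A separate simulation of 90 patients, with a covariate correlated 0.4 with slope, gave 1.0916 falling to 1.0647, a 2.5% reduction.

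**The case against.** - **The form of the primary covariates is not stated.** A reader might infer that the primary model enters its covariates in a way that cannot adjust the slope. The documents do not support that. SAP 8 and 8.1 do not spell out the treatment, time or random terms of that model either, so silence about covariate-by-time terms is not a decision against them. Even main effects act a little if the slopes pass through the origin, which is plausible for a change-from-baseline outcome. This objection stands; what remains is that the form must be stated.
- **The median split.** The wording leaves open whether the split applies to every covariate or only to the three biomarkers, so the documents do not show that FVC, DLCO and age are dichotomised.
- **Longer-term FVC is partly covered.** SAP 8.1 extends the covariate-adjusted strategy to Part B. That stands in part: the extension sits in the analysis that omits spirometry after the dose switch. The all-study model keeps those data and is unadjusted.
- **Limited consequence.** This is a Phase 1b study with safety as its primary objective, SAP 6.1 plans no formal hypothesis tests, and stratified randomisation already limits Part A imbalance on region and severity. All true, and they make this a matter of efficiency. They do not explain why the DLCO model differs from the cough and HRCT models.
- **Large gains cannot be claimed.** A reader might infer a saving of 10% or more in patients. That would need an assumed explained variance for which the documents give no figure.
- **Timing.** SAP 3.0 is dated 15 July 2021; the DSMB compared the doses on 12 October 2020. Choosing covariates after that review in an open-label trial needs care. This stands and shapes the fix.

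**Conclusion.** The point holds for two models. The DLCO model and the all-study in-clinic FVC model omit the outcome's baseline value, region and FVC severity, without explanation and out of line with the SAP's own cough and HRCT models.

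The effect is lost precision and weaker protection against chance imbalance. It is not bias in the randomised Part A comparison, and it does not affect the error rate of a formal between-arm test, since none is planned. Its size is unknown. The FVC illustration rests on the planning SD of 4.5 and an assumed correlation, and shows a modest gain that vanishes as the correlation approaches zero.

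For the primary slope model the finding is one of specification. If the covariates are main effects in a model with a free intercept, the slope difference is essentially unadjusted; if they are crossed with time, it is adjusted. The SAP does not say which.

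**What to change.** 1. In the DLCO model (SAP 8.2.6) and the all-study in-clinic FVC model (SAP 8.1), add the baseline value of the outcome, region and FVC severity. Severity may be the below-50% / 50%-or-above stratum or, as at most 20 patients fall below 50%, continuous baseline FVC % predicted.
2. Add a baseline-by-time term to both models, so that the adjustment reaches the treatment-by-time contrast as well as the level.
3. In the primary model (SAP 8 and 8.1), state the form of each covariate. Either specify covariate-by-time terms for baseline FVC and region, or define the result as a Week 24 contrast that main effects can adjust. Say which covariates are split at the median.
4. Report the adjusted models alongside those now specified, and note that the change was made after the DSMB's dose comparison.

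The cost is SAP wording, model code and a few degrees of freedom. All the variables are already collected.

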10.1. Adverse Events / Adverse Drug Reactions

An adverse event (AE) is any untoward medical condition that occurs in a patient while participating in this clinical study. Adverse events will be coded according to the Medical Dictionary for Regulatory Activities (MedDRA 21.1 or higher) terminology and the severity of the toxicities will be graded according to the National Cancer Institute (NCI) Common Terminology Criteria for Adverse Events (CTCAE), v5.0, where applicable. An adverse drug reaction (ADR) means any AE caused by a drug or biologic.

Treatment-Emergent Adverse Events (TEAEs) are those adverse events/adverse drug reactions that are recorded during or following the initiation of AP01 medication administration, and do not necessarily have a causal relationship to the use of the study medication. Treatment-Emergent Adverse Events (simply referred to as adverse events in summary tables) will be summarized.

The following adverse event summary tables will be summarized by treatment group and combined over both treatment groups:

- 1) An overall summary with the number and percentage of patients reporting AEs, serious AEs, grade 3 or higher AEs, treatment-related AEs, AEs leading to study treatment (AP01) discontinuation and AEs with outcome of deaths. In addition, this overall summary will be performed for each subgroup listed in Section 6.6.
- 2) AEs overall and by system organ class and preferred term. In this summary, a patient is counted once at the system organ class and once at each preferred term within the system organ class. In addition, this summary will be performed for each subgroup listed in Section 6.6.
- 3) A separate summary of respiratory [SOC respiratory, thoracic and mediastinal disorders] TEAEs by Preferred Term and summary of tolerability including cough due to drug administration and bronchospasm after in-clinic drug administration) will be performed by each subgroup listed in Section 6.6.

This document is confidential.

Statistical Analysis PlanSponsor: Avalyn Pharma, Inc.; Protocol No.: AP01-002

- 4) AEs overall and by system organ class, preferred term and highest CTCAE grade.

In this summary, a patient is counted once at the highest grade for which the event occurred in the system organ class and the highest grade for each unique preferred term within that system organ class. Therefore, patients may only contribute once to each preferred term and once to each system organ class. The missing severity grade will be reported in a separate category.

- 5) Study-treatment-related AEs overall and by system organ class and preferred term.

All those AEs with relationship to AP01 marked as “Possibly Related” or “Probably Related” or missing will be reported in the table.

- 6) Study-treatment related AEs by system organ class, preferred term and Highest CTCAE grade
- 7) AEs leading to study treatment termination by system organ class and preferred term
- 8) AEs leading to study treatment termination by system organ class, preferred term and highest CTCAE grade
- 9) CTCAE Grade 3 or higher AEs, overall and by system organ class and preferred term

A Serious Adverse Event (SAE) is an AE that falls into one or more of the following categories:

- a. Results in death
- b. Is life-threatening
- c. Requires inpatient hospitalization or prolongation of existing hospitalization
- d. Results in persistent or significant disability or incapacity
- e. Is a congenital anomaly/birth defect
- f. Is any other important medical event

Serious adverse events will be summarized by treatment group and combined over both treatment groups.

- 1) SAEs overall and by system organ class and preferred term.

In this summary, a patient is counted once at the system organ class and once at each preferred term within the system organ class.

- 2) SAEs overall and by system organ class, preferred term and highest CTCAE grade.

